	
Exclusion criteria
 
They will be excluded from the study patients:
 
 
1. with any active or chronic infection or diseases other than MS, including but not limited to infection with HIV1-2, Hepatitis B or Hepatitis C and tuberculosis or immune deficiency syndromes;
 
2. treated with any immunosuppressive therapy, including but not limited to natalizumab and fingolimod, within the 3 months prior to screening;
 
3. treated with interferon-beta or glatiramer acetate within the 30 days prior to screening;
 
4. treated with corticosteroids within the 30 days prior to screening;
 
5. if relapse occurred during the 30 days prior to screening;
 
6. with contraindications for or intolerance to any medication, treatments and procedures that will be used in the study;
 
7. pregnant or in lactation or of childbearing age who are not willing to use a contraceptive method effective* for the entire duration of the study;
 
8. who, in the opinion of the investigator, showing any condition that would preclude study participation.
 
 
* refer to guideline  http://www.hma.eu/fileadmin/dateien/Human_Medicines/01_About_HMA/Working_Groups/CTFG/2014_09_HMA_CTFG_Contraception.pdf

Sample size
	
Max 24 patients (max 6 patients for each cohort)

Accrual/duration timeline
	
Start: 2017
 
Recruitment period:
 
For each subject the study phase will be completed after 96 weeks follow up after ATIMP administration.

Statistical considerations
	
Descriptive statistics (including means, standard deviations, and medians for continuous variables and proportions for discrete variables) will be used to summarize data as appropriate. A statistical analysis plan (SAP) with detailed statistical methods and techniques used for data analysis will be prepared before conducting the analysis.

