#### 7.10 Methods of assigning patients to treatment groups

The protocol will consist of a total of four TC (from A to D), each of which receiving a single escalating dose of hNPCs injected intrathecally as it follows:

- TC-A:  $0.7 \times 10^6 \pm 10\%$  cells/kg of body weight;
- TC-B:  $1.4 \times 10^6 \pm 10\%$  cells/kg of body weight;
- TC-C:  $2.8 \times 10^6 \pm 10\%$  cells/kg of body weight;
- TC-D:  $5.7 \times 10^6 \pm 10\%$  cells/kg of body weight.

The trial will start with TC-A and will go through the subsequent enrolment of patients to be included in TCs from B to D.

Each cohort will consist of three patients at minimum. However in case of safety issue the numerosity of each TC will be increased to six patients, as explained below.

We define a DLT any adverse event of grade 3 possibly related to hNPCs or to the procedure. However we will not consider a DLT a prolonged hospitalization due to post lumbar puncture headache if not associated to any meningeal sign. We will not considered DLT adverse events related to concomitant treatments (tacrolimus and steroids)

After the inclusion of the first patient of the TC we will wait at least 14 days to treat the second patient. The same interval time will be used for all the further patients within the same TC. After the inclusion of all the planned patients within a TC, we will wait at least 3 months after the inclusion of the last patient before switching to the higher TC.

In case of none DLT within the TC, we will wait at least 3 months after the inclusion of the last patient and then we will move to the higher TC.

In case of 1 DLT within the TC, the cohort will be extended to 6 patients. If another DLT will be observed, the current dosage will be considered excessive and the immediate lower dosage will be considered MTD.

The safety monitoring board will review all safety data in the case of an AE  $\geq 3$  evaluated “possibly related to hNPC” by investigators and in any case before the shifts between TCs.

This will be repeated for every TC up to the end of the study.

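### The MTD rule in section 7.10 can name a dose on the evidence of three patients, and names a dose that does not exist if the lowest cohort is excessive

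*Combined protocol and SAP*

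**What the plan says.** All of the rule is in section 7.10 of the protocol.

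- **Dose levels.** "The protocol will consist of a total of four TC (from A to D"). Escalation begins at the bottom: "The trial will start with TC-A and will go through the subsequent enrolment of patients to be included in TCs from B to D". No dose below TC-A is defined anywhere.
- **Cohort size.** "Each cohort will consist of three patients at minimum". The text adds that a safety issue leads to six patients, and refers for this to the rule that follows it.
- **No DLT.** The team waits at least three months "after the inclusion of the last patient and then we will move to the higher TC". No expansion is required.
- **One DLT.** "In case of 1 DLT within the TC, the cohort will be extended to 6 patients". This is the only stated trigger for expansion.
- **A further DLT.** "If another DLT will be observed, the current dosage will be considered excessive and the immediate lower dosage will be considered MTD".
- **Scope.** The section closes by applying the same procedure to each cohort in turn, without an exception for TC-A.

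The synopsis (section 1.1, Sample size) sets the limit: "Max 24 patients (max 6 patients for each cohort"). Section 11 promises descriptive statistics and a later SAP. It gives no target DLT rate and no method for estimating an MTD.

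**The concern.** The MTD sentence fixes a formal conclusion but attaches no evidence requirement to it. The trigger lies in the higher cohort and the label goes to the lower one. If the lower cohort passed on 0/3, it is named MTD without any further observation, and the reader of the report is not told that three patients stand behind the term.

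The sentence also assumes that a lower dose always exists. For TC-A it does not, so the rule as written returns no valid result in exactly the case where the starting dose proves excessive.

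Section 5.5.1 describes the safety profile of these cells as unknown and says they have not been used in multiple sclerosis before. A reader of the results may therefore take the MTD label at face value.

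**Working it through.** **Inputs from the documents.** Four dose levels, at least three and at most six patients per cohort, expansion after one DLT in the same cohort (section 7.10; synopsis 1.1). The plan's own figure reproduces: 4 × 6 = 24. If all four cohorts are completed, the minimum is 4 × 3 = 12.

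**Assumptions.** The documents give no DLT rates, so every rate below is assumed. Cohorts without a DLT are taken to close at three. Two readings are left implicit in the text: 1/6 allows escalation, and two or more DLTs among the first three make the dose excessive. Neither reading creates the problem.

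**What 0/3 shows.** The exact two-sided 95% upper limit is 1 − 0.025^(1/3) = 0.708, so the CI is 0–71%. A dose with a true DLT rate of 30% gives 0/3 with probability 0.7³ = 34%.

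**Path probabilities for a cohort with true DLT rate p.**

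- Passes on three patients: a = (1−p)³
- Passes on six patients (1/3, then 0/3): b = 3p(1−p)² × (1−p)³
- Excessive: e = 1 − a − b

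| Cohort | p | a | b | e |
|---|---|---|---|---|
| TC-A | 0.05 | 0.857 | 0.116 | 0.027 |
| TC-B | 0.10 | 0.729 | 0.177 | 0.094 |
| TC-C | 0.20 | 0.512 | 0.197 | 0.291 |
| TC-D | 0.35 | 0.275 | 0.122 | 0.604 |

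**Probability that each dose is named MTD.** This is the chance of reaching the next cohort times e for that cohort. The part resting on three patients is that value times a/(a+b) of the named dose.

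| Dose named MTD | Reach next × e | Probability | Share on three, a/(a+b) | On three patients |
|---|---|---|---|---|
| TC-A | 0.973 × 0.094 | 0.091 | 0.881 | 0.081 |
| TC-B | 0.882 × 0.291 | 0.257 | 0.805 | 0.207 |
| TC-C | 0.625 × 0.604 | 0.377 | 0.723 | 0.273 |
| Total | | 0.726 | | 0.560 |

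An MTD is declared in 73% of trials, and 0.560 / 0.726 = 77% of these rest on three patients. In the remaining trials TC-A is excessive (2.7%) or TC-D passes (24.8%).

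**Other assumed scenarios, TC-A to TC-D.**

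| Rates | MTD on three | MTD on six | Share on three |
|---|---|---|---|
| 5/10/20/30% | 0.516 | 0.149 | 78% |
| 10/20/30/40% | 0.599 | 0.209 | 74% |
| 20/30/40/50% | 0.489 | 0.201 | 71% |

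**TC-A excessive (e for the first cohort).** At assumed TC-A rates of 5%, 10%, 20% and 30%, e is 0.027, 0.094, 0.291 and 0.506: 3%, 9%, 29% and 51% of trials. In each of these the rule points to a dose that is not in the protocol.

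**The case against.** The strongest reply is that finding an MTD is not what this trial sets out to do. Section 4.1 names feasibility, safety and tolerability, the endpoints in section 5.3 do not include an MTD, and the analysis is descriptive. The safety board reviews all data before each move between cohorts, and section 6.3.1.2 allows suspension or termination for unacceptable risk. This stands as a limit on the consequence. It does not supply a minimum number of patients for the label, nor the conclusion to be reported if TC-A is excessive.

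It can also be said that three is only a minimum, and that a safety issue leads to six. But that sentence defers to the detailed rule, which expands only the cohort in which the DLT occurred. A lower cohort that itself had one DLT would already have six patients, so the weakness affects many MTD declarations, not all.

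Three stronger readings are tempting, and the documents do not support them.

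- *That an MTD should require six patients with at most one DLT, and that this would settle the matter.* The gain is moderate. At a true DLT rate of 40% the present rule clears a dose with probability 0.216 + 0.093 = 31%. At most 1/6 would clear it with probability 0.6⁶ + 6 × 0.4 × 0.6⁵ = 23%. After 1/6 the exact two-sided upper limit is still 64%. Such a rule would also need a provision for a refilled cohort that then fails. It concerns dose assignment and is for the sponsor.
- *That the rule contradicts itself if TC-D passes.* It does not. The MTD sentence depends on a further DLT, so no MTD is then declared. Only an explicit statement is missing.
- *That the MTD found here will be the dose of later studies.* The documents do not say so.

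**Conclusion.** The point holds as a defect in a stated rule. Section 7.10 can attach the term MTD to a dose on 0/3, where DLT rates up to 71% remain within the exact 95% CI. In the four assumed scenarios, 71–78% of declared MTDs rest on three patients. Those shares depend on the assumed rates and on the two implicit readings, but the possibility of a three-patient MTD follows from the text alone.

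The undefined dose below TC-A also follows from the text alone. How often it would matter depends on the true TC-A rate: 3% of trials at 5%, rising to 51% at 30%.

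The importance is moderate, because the MTD is not a stated objective. A reader might infer that an excessive TC-A leaves the trial without any way to stop. That is not so: the termination provisions apply, and what is missing is the conclusion to be reported.

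**What to change.** Amend the MTD sentence in section 7.10, and carry the same wording into the SAP:

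- (a) If the next lower dose passed on 0/3, report it as *highest dose with 0/3 DLT, 95% CI 0–71%*, not as an established MTD. Report any declared MTD with its number treated, DLT count and exact CI.
- (b) If TC-A is excessive, the conclusion is *MTD not established; below the lowest dose tested*.
- For clarity only, state *MTD not reached* if TC-D passes.

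Whether to treat further patients at the lower dose before using the term MTD, within the stated maximum of six per cohort and 24 in total, is for the sponsor to decide and to reconcile in section 7.10.

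The changes in (a) and (b) are wording only, with no added patients and no added time. The price is a less definite MTD label.

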**AEs related to lumbar puncture and injection procedure:**

Lumbar puncture: is a minimally invasive, diagnostic or therapeutic procedure that involves the removal of a small amount of cerebrospinal fluid (CSF) - the fluid that surrounds the brain and spinal cord - followed by the injection of neural cells into the lumbar region of the spinal column. In this study, the quantity of collected CSF will be replaced by the same amount of cell culture medium.

The most frequent adverse events related to this procedure is the orthostatic headache and/or back pain. The frequency of these events is about 15-30%. Normally they resolve in few days and they can be treated with bed rest, anti-inflammatory drugs and hydration. The injection of any substance in the spinal canal could induce an inflammatory/irritative reaction with highly variable severity and duration of the AE. This kind of reaction is unpredictable.

Overall, rare adverse events (<1%) are related to the simple Lumbar Puncture Procedure and consist in: risk of infection; risk of bleeding (epidural or subdural hematoma); risk of cranial nerve palsy and cauda equina syndrome; hypotension, bradycardia with or without syncope.

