**Infective Complication due to Immunosuppressive treatments**

To address the risk of opportunistic infections and organ toxicity due to combined steroid and tacrolimus treatment, periodic clinical, biochemical (full blood count, renal and liver function) drug level (FK506), immunological and virological monitoring (PCR for cytomegalovirus-CMV and Epstein virus-EBV) will be instituted at fixed intervals (see details in the specific chapter) and depending on patient's clinical and biochemical condition and previous findings, for the entire duration of the immunosuppressive treatment.

Pre-emptive CMV reactivation will be treated by standard treatment for immunosuppressed patients (i.e. ganciclovir or foscarnet). Immunosuppression reduction or discontinuation can be considered depending on severity.

EBV reactivation will be treated with immunosuppressive drug reduction or discontinuation and/or anti-CD20 (Rituximab) depending on the copy level and patient's clinical condition.

Recurrent episodes of CMV reactivation will be addressed with reduction of the immunosuppressive drug tacrolimus. Immunosuppression discontinuation will be considered depending on severity.

Bacterial infection will be treated according to standards. Repeated infections will be addressed by reduction or discontinuation of immunosuppression depending on site of infection, severity and patient's condition.

The safety profile related to concomitant medication will be assessed through general physical examination, neurological visit and through blood examination specifically hematology and chemistry parameters. At every visit signs and symptoms of possible infective events will be recorded.

For all the concomitant medication and procedure used in the protocol only AEs exceeding the grade 3 of severity according to the international definition of AEs will be reported (see also CTCAE).

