**5.5.2.2 Forwarding**

All the Serious AE (SAE) and the ADR will be notified, as specified in Table 2.

	Documentation	Report	Time
Serious (AE, ADR)	Patient's chart CRF SAE-Form	Investigator forwards SAE-form to Local E.C.	Within 24 h
Non-serious (AE, ADR)	Patient's chart	-	-

Table 2 – SAE/ADR timeline

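### Section 7.10 orders a board review after a serious-grade cell-related event but does not make the next same-dose injection wait for it, and the review trigger is narrower than the DLT definition

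*Combined protocol and SAP*

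**What the plan says.** All the dosing rules are in section 7.10.

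- **DLT definition:** "We define a DLT any adverse event of grade 3 possibly related to hNPCs or to the procedure". There is one relevant exemption: "However we will not consider a DLT a prolonged hospitalization due to post lumbar puncture headache if not associated to any meningeal sign". Events due to tacrolimus or steroids are also excluded.
- **Spacing:** "After the inclusion of the first patient of the TC we will wait at least 14 days to treat the second patient". The same interval applies to later patients in the cohort. Moving up a dose requires at least three months after the last patient's inclusion.
- **After one DLT:** "In case of 1 DLT within the TC, the cohort will be extended to 6 patients". A second DLT makes the dose excessive, and the next lower dose becomes the MTD.
- **Board review:** "The safety monitoring board will review all safety data in the case of an AE" of grade 3 or above judged possibly related to hNPC, and in any case before each move between cohorts.

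Elsewhere, section 5.5.1 describes the safety profile of the cells as unknown. Section 5.5.2, on the lumbar puncture and injection, warns: "The injection of any substance in the spinal canal could induce an inflammatory/irritative reaction", and calls this kind of reaction unpredictable.

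**The concern.** The cells are given once and cannot be taken back. For the next patient, the main protection is therefore the decision whether to inject at all. A review that may finish after that injection cannot inform the decision, and nothing in 7.10 ties the two together.

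The second issue is who decides that the board looks. A DLT may be related to the cells or to the procedure, but the event-driven review is triggered only by relation to the cells. The investigators' own attribution therefore determines whether an independent body sees the event promptly. Cells and puncture are delivered in one act, so this attribution is hard to make, and an outside check is most useful before the next patient is treated.

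**Working it through.** **Plan's own figure.** Four cohorts of at most six patients: 4 × 6 = 24, which matches the stated maximum (Synopsis and section 8.1).

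**Step 1: the rules of 7.10 side by side.**

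| Grade 3 event | DLT? | First one extends cohort to six? | Event-driven review? | Next injection held? |
|---|---|---|---|---|
| Possibly related to hNPC | Yes | Yes | Yes | Not stated |
| Related to procedure only | Yes | Yes | No | Not stated |

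For the second row, the first required review is the one before a cohort shift. TC-D has no higher cohort, and a second DLT ends escalation. In those two situations no review of a procedure-only DLT is explicitly required.

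**Step 2: is a hold supplied elsewhere?**

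- Section 5.5.2.2, Table 2, for serious events: "Investigator forwards SAE-form to Local E.C", within 24 hours. Section 5.5.7 adds immediate reporting to the sponsor. The board is not named and dosing is not stopped. For non-serious events Table 2 gives no reporting route.
- Section 5.5.2, end of the paragraphs on infective complications: "For all the concomitant medication and procedure used in the protocol only AEs exceeding the grade 3 of severity" are to be reported. If this covers the study puncture, a grade 3 procedure-only DLT falls below the threshold. The wording is ambiguous on that, and 5.5.7 still has every AE recorded in the CRF.
- Section 6.3.1.2 allows suspension, but starting one is discretionary.
- Section 9.7 asks for rapid-termination mechanisms without setting any. Section 10.5, on the board's procedures, is still a template prompt.

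None of these is a binding hold.

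**Step 3: when the 14 days start.** Section 7.10 counts from inclusion. Sections 8.3.1 to 8.3.3 place inclusion at the end of screening, before the pre-treatment phase, and tacrolimus starts on day -7 (section 7.2). If inclusion falls on day -7, the gap between injections could be 14 − 7 = 7 days. The counts below use 14 days between injections, which is the more favourable reading.

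**Step 4: injections permitted.** After a DLT in patient 1, 6 − 1 = 5 further same-dose injections are allowed (days 14, 28, 42, 56 and 70) unless a second DLT occurs.

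Let the event fall on day d (1 to 13) and the review take W days. The protocol gives no review time, so W is assumed. Count the k with d ≤ 14k < d + W.

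- W = 7: day 14 is caught only if d > 7. Result: 0 for d = 1–7, 1 for d = 8–13.
- W = 14: day 14 is always caught and day 28 never. Result: 1.
- W = 28: days 14 and 28 are always caught and day 42 never. Result: 2.

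**Step 5: chance of a further DLT among those patients.** This is 1 − (1 − p)^n, with independent patients and a per-patient DLT probability p that the documents do not give.

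| p (assumed) | n = 1 | n = 2 |
|---|---|---|
| 5% | 5% | 1 − 0.95² = 10% |
| 20% | 20% | 1 − 0.80² = 36% |
| One third | 33% | 1 − (2/3)² = 56% |

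These are upper limits on what a hold could avert, since the board might recommend continuing.

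**The case against.** The strongest reply is that the plan already has the means to stop. Section 6.3.1.2 lists unacceptable risk as a ground for suspension and allows resumption only once concerns have been addressed to the satisfaction of the sponsor, ethics committee or authority. Once started, that is a real hold. This stands, but someone must choose to start it, and 7.10 does not require that.

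The second reply is that the procedure-only case is thin. Under section 5.5.3.1 an event is possible when the alternative explanation is inconclusive and causality cannot be excluded. With cells and puncture given together, many procedural DLTs would also be rated possibly related to hNPC and would trigger the review. This stands too, and that part of the point is narrow.

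Third, section 5.5.1 reports no related adverse events in 42 patients given hNPCs. Those patients had surgical injection into brain or cord, and the same section mentions two late graft-derived tumours in other studies. The record argues against assuming only high DLT rates, which is why the range starts at 5%.

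Some stronger readings are tempting but unsupported:

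- A reader might infer that a procedure-only DLT is never reviewed. The review before a cohort shift covers all safety data where there is a shift.
- A reader might infer that dosing must continue during a review. The plan permits this but does not require it.
- A reader might use the 24 patients per year in section 14 to set the spacing within a cohort. That figure is an estimate of enrolment potential and says nothing about spacing.

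**Conclusion.** The point holds. As written, 7.10 allows an irreversible same-dose injection while a DLT is still unreviewed, and its event-driven trigger does not cover every DLT. Both follow from the text and depend on no assumption.

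The size is illustrative. With injections 14 days apart and review times of 7 to 28 days, 0 to 2 patients could be injected during a pending review. At assumed DLT probabilities of 5% to one third, the chance that at least one of them has a DLT is 5–33% for one injection and 10–56% for two. If the interval really runs from inclusion, exposure could be somewhat greater. The finding does not show that the plan is unsafe or that a pause would be refused. It shows that a pause is left to discretion where a rule would be easy to write. This is a cheap improvement.

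**What to change.** In section 7.10:

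1. Make the event-driven review cover every DLT, meaning grade 3 or higher and related to hNPC or to the procedure, as well as any AE of grade 3 or above possibly related to hNPC. Keep the headache exemption. State that every DLT is reported to the board whatever the threshold in section 5.5.2.
2. Give no further injection until the board's written recommendation is filed, within a review period fixed in advance (for example 14 days). Apply this also to late events in earlier cohorts.
3. Count the 14-day interval from the previous patient's injection.
4. If the next patient has not begun tacrolimus, do not start it. If it has begun, continue it under the level monitoring of section 7.2 up to a set limit. State that a held patient is not withdrawn under section 6.3. State also that, on any re-screening, protocol-given tacrolimus and steroids do not count under exclusions 2 and 4.

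**Cost.** A few sentences. For an event on day d (1 to 13) and a 14-day review, the delay is d + 14 − 14 = d, so 1 to 13 days. For a late event it is up to about two weeks. This lies within the 15 ± 3 days (12 to 18) that section 7.1 already accepts after a traumatic puncture, when tacrolimus is under way. The screening window of days -28 to -7 is 21 days, the same as the three-week screening phase, so some patients may need tests repeated and one may occasionally be lost. Maximum enrolment stays at 24.

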**5.5.3 Adverse Drug Reaction (ADR)**

An Adverse reaction (ADR): all untoward and unintended responses to an investigational medicinal product related to any dose administered. The phrase responses to an investigational medicinal product means that a causal relationship between the investigational medicinal product and an adverse event is at least a reasonable possibility, i.e. the relationship cannot be ruled out.

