### 5.5.3.1 Attribution Definitions

**Not related:** An adverse event that is not related to the use of the investigational product.

**Doubtful:** An AE for which an alternative explanation is more likely, e.g., concomitant drug(s), concomitant disease(s), or the relationship in time suggests that a causal relationship is unlikely.

**Possible:** An AE that might be due to the use of the investigational product. An alternative explanation, e.g., concomitant drug(s), concomitant disease(s), is inconclusive. The relationship in time is reasonable; therefore, the causal relationship cannot be excluded.

**Probable:** An AE that might be due to the use of the investigational product. The relationship in time is suggestive (e.g., confirmed by de-challenge). An alternative explanation is less likely, e.g., concomitant drug(s), concomitant disease(s).

**Very likely:** An AE that is listed as a possible adverse event reaction, and cannot be reasonably explained by an alternative explanation, e.g., concomitant investigational drug(s), concomitant disease(s). The relationship in time is very suggestive (e.g., it is confirmed by de-challenge and re-challenge).

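### Only the investigators' own rating brings a grade 3 or higher event to the safety board early; an event they rate Doubtful waits by default for the cohort shift, and TC-D has no later shift

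*Combined protocol and SAP*

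**What the plan says.** Section 7.10 gives the board two occasions to look. The first is event-driven: "The safety monitoring board will review all safety data in the case of an AE" of grade 3 or higher that has been rated possibly related to hNPC. The second is scheduled. The sentence closes with who does the rating and when else the board meets: "by investigators and in any case before the shifts between TCs".

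The same section defines the dose-limiting event more widely: "We define a DLT any adverse event of grade 3 possibly related to hNPCs or to the procedure". Within a cohort, after the first patient, "we will wait at least 14 days to treat the second patient", and the same gap applies to later patients. The next cohort opens at least 3 months after the last patient of the current one.

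Section 5.5.3.1 has five attribution levels. *Doubtful* lies one step below *Possible* and is defined as "An AE for which an alternative explanation is more likely", or one where "the relationship in time suggests that a causal relationship is unlikely". *Possible* is the lowest level at which causality is kept open: "The relationship in time is reasonable; therefore, the causal relationship cannot be excluded".

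Serious events go to the local ethics committee within 24 hours (section 5.5.2.2, Table 2) and immediately to the sponsor and ethics committee (section 5.5.7). Neither section names the board. Section 10.5, where the board's operating rules belong, still holds a template instruction to specify them.

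**The concern.** The event trigger depends on a judgement made by investigators who know the dose, in a trial with no control group to show the background rate. Section 5.5.1 states that the safety profile of the cells is unknown and that they have never been used in MS. Section 5.5.2 lists neurological events such as seizures, encephalopathy and mental status changes as expected with tacrolimus, which all patients are to receive. An alternative explanation will often be available, and where the investigators judge it the more likely one, the rating is *Doubtful*.

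Such an event is neither a DLT nor a reason to call the board. What is at stake is whether an independent body can look at it before further patients receive the same dose, and whether it looks at all during TC-D, the highest dose.

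**Working it through.** **The plan's own figure.** Four cohorts × 6 patients = 24, which matches the stated maximum. The point does not depend on it.

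**Route of a grade 3 or higher event, by attribution (sections 7.10, 5.5.2.2, 5.5.7)**

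| Investigators' rating | Counts as DLT under 7.10 | Triggers the board | Sponsor and ethics committee, if serious |
|---|---|---|---|
| At least *Possible*, to hNPC | Yes, subject to 7.10's exclusions | Yes | At once |
| At least *Possible*, to the procedure only | Yes, subject to 7.10's exclusions | No | At once |
| *Doubtful* or *Not related* | No | No | At once |

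The second row follows because the trigger names only hNPC, while the DLT definition names hNPCs or the procedure.

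**Timing.** Inputs: minimum spacing of 14 days and at least 3 months after the last patient (section 7.10). I take 3 months as 90 days.

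- Last injection = 14 × (n − 1). For n = 3: day 28. For n = 6: day 70.
- Earliest shift = last injection + 90. For n = 3: 28 + 90 = day 118. For n = 6: 70 + 90 = day 160.
- In a three-patient cohort, a *Doubtful* event in patient 1 before day 14 can be followed by two more injections before any scheduled board review. Between days 14 and 28 it can be followed by one, and after day 28 by none.
- The protocol places the review before the shift but gives it no date, so day 118 is the earliest shift and not a fixed review day.
- After TC-D there is no shift, so this calculation yields no scheduled review for that cohort.

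**Cost of a wider trigger.** Assumption, not in the documents: 0.5 to 1 grade 3 or higher event per patient-year that the present trigger would not catch. Patient-time runs from injection to the earliest shift.

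- Three patients: 118 + 104 + 90 = 312 days; 312 / 365.25 = 0.85 patient-years. Extra reviews: 0.85 × 0.5 = 0.43 to 0.85 × 1 = 0.85, about 0.4 to 0.9.
- Six patients: 160 + 146 + 132 + 118 + 104 + 90 = 750 days; 750 / 365.25 = 2.05 patient-years. Extra reviews: 2.05 × 0.5 = 1.03 to 2.05 × 1 = 2.05, about 1 to 2.

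**The case against.** The strongest reply is that the board reviews all safety data before every higher dose, *Doubtful* events included. This stands. A reader might infer that investigator attribution alone decides escalation; the documents do not support that. Section 10.5 leaves the board's powers unstated, so nothing shows that it could not hold a shift.

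For the same reason, escalation probabilities should not be used as the size of the problem. With an assumed true rate of 33%, the chance of no counted DLT in three patients is (1 − 0.33)³ = 30%. It becomes (1 − 0.33 × 0.75)³ = 43% if a quarter of events are rated below *Possible*, and (1 − 0.33 × 0.5)³ = 58% if half are. Those misrating shares are invented for illustration, and the calculation treats the count as the decision, as though the shift review did not exist.

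A reader might also infer that all six patients of an expanded cohort are routinely injected by day 70 unseen by the board. That mostly fails. Expansion follows a DLT, and a DLT rated possibly related to hNPC triggers review of all safety data, earlier *Doubtful* events included. The exceptions are a DLT attributed only to the procedure, or a *Doubtful* event that arises after the triggered review.

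Nor do the documents clearly contradict themselves on *Doubtful*. Section 5.5.3 ends its definition of a reaction with "i.e. the relationship cannot be ruled out", but the same sentence first requires at least a reasonable possibility of causality, and section 5.5.3.1 reserves the matching language for *Possible*. An available alternative does not by itself make an event *Doubtful*; it must be the more likely explanation.

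Other oversight remains: serious events reach the sponsor and ethics committee at once, and section 6.3.1.2 allows suspension for unacceptable risk. Section 7.10 also says that its procedure is repeated for every cohort. Since the scheduled review is tied to a shift, that sentence does not place one in TC-D.

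**Conclusion.** The point holds as a gap in routing and timing. A lone grade 3 or higher event rated *Doubtful* or *Not related* has no stated path to the board before the pre-shift review. In a three-patient cohort at minimum spacing, up to two more patients can be injected in the meantime, by day 28, with the shift at about day 118 or later. For TC-D no scheduled board review is stated. The event trigger is also narrower than the DLT definition beside it, so a procedure-only DLT can expand a cohort without calling the board.

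This is the default path and not a certainty: any other event in the cohort that does trigger the board exposes the *Doubtful* one too. The day counts assume minimum spacing and 90 days for 3 months. The documents do not show that a toxic dose would be passed, or that the board could not act once informed. The change is worth making because it is cheap and protects later patients in the first use of these cells in MS.

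**What to change.** - In section 7.10, send every adverse event of grade 3 or higher to the board promptly, whatever the investigators' attribution, at least until that cohort's shift decision (for TC-D, until the review in the third item).
- Align the trigger with the DLT wording, so that it covers events related to hNPCs or to the procedure.
- State a board review after the last TC-D patient.
- Reconcile sections 5.5.2.2, 5.5.7, 7.10 and 10.5 on how events reach the board, and complete section 10.5.

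Leave the DLT definition and count unchanged. Counting the more conservative of the board's and the investigators' ratings would alter cohort expansion and the MTD, and would add false DLTs, a cost the routing change does not carry.

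The change needs no new body and no new data. Its downside is some extra ad hoc reviews before the shift: about 0.4 to 0.9 per three-patient cohort and 1 to 2 per six-patient cohort, at the assumed 0.5 to 1 event per patient-year.
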